Airway pressure and peak expiratory airflow rate measurements during hospital out-patient visits.

Approximately 3-4 weeks after implantation of the SCS system, all subjects will return to the hospital for the initial application of electrical stimulation on an outpatient basis. At this time, cardiac rate and rhythm, oxygen saturation, and blood pressure will be monitored. All measurements will be made in the sitting posture. Airway pressure and peak expiratory airflow rate will be measured (connection will be made either with a facemask or tracheostomy tube), with a Biopac Data Acquisition System (Biopac Systems MP100).

- Airway pressure. Changes in airway pressure during expiratory efforts are reflective of the pressure developed within the major airways and will be used as an index of the force of expiratory muscle contraction. Prior to SCS, the subject will be asked to relax completely to assure absence of respiratory muscle activation. SCS will be applied for 0.6-0.8s during which time airway pressure will be recorded during airway occlusion.

- Expiratory airflow rate. Peak expiratory airflow rate is also a useful index of cough efficacy and will be monitored in each subject. Inspired and expired volume will be obtained by integration of the airflow signal. Peak expiratory airflow rate will be measured during SCS following release of occlusion.

- Effects of lung volume changes. Airway pressure generation will be assessed at both FRC and TLC. SCS will be applied at each of these lung volumes while measurements of airway pressure and peak expiratory airflow rates are made by the methods described above.

Measurements will also be made with the subject making their own expiratory effort in synchrony with activation of the expiratory muscles by the stimulation system. The subject will be asked to exhale forcefully against an occluded airway in synchrony with muscle activation during which time airway pressure and peak expiratory airflow rate will be monitored. This is the prescribed pattern of use of the system at home by the subject in order to cough and clear their airways.

Assessment of Clinical Outcome Parameters

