The surgical procedures will be performed by [name], staff physician in the Department of Anesthesiology and/or [name], staff physician in the Department of Neurosciences, both at MetroHealth Medical Center. [name] has performed parallel wire lead placement routinely for other indications of SCS for more than 20 years. [name] has implanted the study device in all 17 of our participants in our previous clinical trial using disc electrodes. All aspects of the surgical procedure are standard. However, the application of the wire leads for the purpose of expiratory muscle stimulation is experimental. The surgical procedures are expected to last 2 hours. Any surgical procedure carries a risk of infection and bleeding. The incidence of infection and excessive blood loss related to this surgery are generally considered to be less than 1%. Although unlikely, there is also a chance that the body will reject the implanted materials which will require their removal. It is possible to develop a pocket of fluid (seroma) around the receiver, and, if infected, the receiver will have to be removed. There is also a rare possibility that the stitches holding the leads and receiver in place will break causing these to shift in position. Other potential risks include lead migration and leakage of cerebrospinal fluid.

3. Risks Associated with Spinal Cord Stimulation

Tetraplegic patients are known to suffer from a condition known as autonomic dysreflexia, a condition characterized by symptoms of headache, blotchy skin and sweating, high blood pressure and bradycardia. These symptoms can be triggered by SCS. In our recent clinical trial, these symptoms occurred in ~ 20% of subjects and subsided quickly with discontinuation of stimulation. There is a remote possibility that bowel or bladder discharge

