will occur due to contraction of the abdominal muscles during stimulation. Of note, there has been no occurrence of this potential complication in our recent clinical trial using disc electrodes for SCS. Some leg movement may occur with T11 stimulation. In our recent clinical trial, this was well tolerated in each subject. Due to improper use of the external transmitter (i.e. maintained in place continuously for days and weeks with tight fitting clothing), the receiver may erode through the skin exposing the subject to the risk of infection. There is the remote possibility of electrically induced tissue damage. This is unlikely since the ranges of stimulus amplitude and pulse width are known to be safe. Moreover, the duration of stimulation is very brief. It is possible that placement of the device may worsen spasticity after implantation. This is rare and may ultimately require removal of the device. Temporary or transient sensory changes, such as electric like sensations, may be present during stimulation. These are uncommon and well tolerated, but can be lessened with changes in the stimulation parameters.

4. Device Malfunction

The most common cause of device malfunction is decoupling of the external transmitter over the implanted receiver. Low battery power can also result in device malfunction. An error on the control box will display if there is low battery power. The battery charge status can be checked at any time on the control box. The occurrence of fibrosis at the electrode-tissue interface could affect the long-term physiologic performance of the device. These damages were not encountered in our recent clinical trial nor highly anticipated since the implanted materials are biologically inert.

Improper activation of the implanted receiver could occur by external sources other than the subject's transmitter. However, this is unlikely since the external transmitter must be placed close to the implanted receiver to power the device.

Precautions to minimize risks

1. Pre-Surgical

During standard blood draws, suitable precautions will be taken to minimize risks of bruising, infection or blockage of the vein.

Because MRI could result in movement of iron-containing objects, precautions will be taken to minimize such events. Loose metal objects, like pocketknives or key chains, will not be allowed in the MRI room. Earplugs will be applied to prevent temporary hearing loss.

2. Surgical

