While the incidence of infection and excessive blood loss related to this surgery are generally considered to be very low, every effort to minimize this risk will be taken before, during, and after the procedure, including administration of antibiotics.

3. Spinal Cord Stimulation

Given the possibility of autonomic dysreflexia in response to SCS, blood pressure and pulse will be monitored closely during hospital out-patient visits and at home during the initial period of SCS. If significant blood pressure changes occur (systolic > 140 mmHg) during SCS or if the subject experiences symptoms of autonomic dysreflexia (AD), stimulation will be stopped until hemodynamic parameters stabilize. Based upon our previous experience, increasing the interval between applied SCS minimizes hemodynamic changes and when signs of AD occur initially, they eventually resolve completely over the subsequent 3-4 weeks such that stimulation can be provided very frequently without untoward effects. However, if signs or symptoms of AD persist, Clinical Practice Guidelines of the Consortium for Spinal Cord Medicine for management of AD will be followed. If necessary, the study will be discontinued.

Given the potential of erosion of the receiver through the skin, the subject's skin will be inspected daily for redness and/or irritation and any abnormalities immediately reported to the study team. The subject and caregiver will be instructed to remove the external transmitter each night, inspect the skin and immediately report any abnormal findings to the study team.

4. Device Malfunction

To prevent decoupling of the external transmitter over the implanted receiver, the subject and caregiver will be provided specific instructions on proper application of the device. Methods to assure maintenance of adequate battery power will also be provided, including instruction on how to check the status of battery charge. The level of applied electrical stimulation will be maintained within specific parameters that are known to be safe and not result in deleterious side effects.

Toxic/hazardous substances

Not applicable

Radiobiological information

Not applicable

Potential benefits

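### The blood-pressure stop during stimulation is described as a change but set only as an absolute systolic level, with no resting reference for stopping or restarting

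*Protocol*

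**What the plan says.** The rule is in the Protocol, section VIII, Precautions to minimize risks, item 3 (Spinal Cord Stimulation). The SAP does not address it.

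- **Trigger.** There are two limbs joined by 'or'. The first is numeric: "If significant blood pressure changes occur (systolic > 140 mmHg) during SCS". The second is that the subject has symptoms of AD.
- **Action and restart.** In either case "stimulation will be stopped until hemodynamic parameters stabilize".
- **Monitoring.** The same item states that "blood pressure and pulse will be monitored closely during hospital out-patient visits and at home during the initial period of SCS". For the first stimulation visit, section VII (Specific Physiologic Measurements) adds: "At this time, cardiac rate and rhythm, oxygen saturation, and blood pressure will be monitored". Neither place names a pre-stimulation reading as the comparator.
- **Escalation.** Outside guidance comes in later: "if signs or symptoms of AD persist, Clinical Practice Guidelines of the Consortium for Spinal Cord Medicine for management of AD will be followed". Discontinuing the study is the last resort.
- **What AD is.** Section VIII, Potential risks, item 3 lists headache, blotchy skin and sweating, and then "high blood pressure and bradycardia. These symptoms can be triggered by SCS". In the earlier disc-electrode trial "these symptoms occurred in ~ 20% of subjects and subsided quickly with discontinuation of stimulation".
- **Eligibility.** Section VI excludes hypertension or hypotension only when it is unmanaged and sets no numeric limit on resting pressure.

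**The concern.** A level and a change are different quantities. A rule meant to catch significant changes, but triggered only by an absolute value, treats the same rise differently according to where the subject starts. It is most permissive in subjects with the lowest resting pressure and most sensitive in those resting just under the ceiling. The eligibility criteria do not rule out a low resting pressure.

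The restart condition has the same weakness. With no reference value, a steady 138 mmHg could be read as stable in a subject who rests at 90.

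What is at stake is subject safety. AD is a stimulation risk that the Protocol itself names, and stopping stimulation is its first response. The reassurance from the earlier trial is that symptoms went away once stimulation stopped, so it depends on a stop being called.

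**Working it through.** The Protocol's 140 mmHg is a chosen threshold, not a derived figure, so there is nothing to reproduce. The check is what the threshold permits.

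**Inputs**
- Numeric trigger: systolic above 140 mmHg (Protocol, section VIII, Precautions, item 3).
- Resting systolic pressure R: not given in either document. Values from 90 to 135 mmHg are assumed.
- Added trigger, a rise of more than X: illustrative 20 to 40 mmHg, not from the documents.
- Restart margin Y above rest: illustrative 10 and 15 mmHg, not from the documents.

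**Step 1. Largest rise that does not meet the present numeric limb = 140 - R**

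| Assumed R (mmHg) | Calculation | Rise allowed (mmHg) |
|---|---|---|
| 90 | 140 - 90 | 50 |
| 100 | 140 - 100 | 40 |
| 110 | 140 - 110 | 30 |
| 120 | 140 - 120 | 20 |
| 130 | 140 - 130 | 10 |
| 135 | 140 - 135 | 5 |

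**Step 2. Does the limb track change?** From 90, a rise of 45 gives 90 + 45 = 135: no stop on the number. From 135, a rise of 6 gives 135 + 6 = 141: stop. The much larger change passes and the smaller one does not.

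**Step 3. What is left at or below 140 mmHg?** Only the symptom limb. Its list includes high blood pressure and bradycardia, and pulse is monitored, so it gives real cover, but it puts no figure on either. The guideline sentence applies once AD persists, so it does not set the first stop. The uncovered case is therefore a large rise ending at 140 mmHg or less without recognised AD symptoms.

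**Step 4. Effect of adding a rise trigger.** The rise allowed becomes min(X, 140 - R). At R = 90:
- X = 20: min(20, 50) = 20
- X = 30: min(30, 50) = 30
- X = 40: min(40, 50) = 40

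The added trigger acts only when R is below 140 - X, that is below 120, 110 or 100 mmHg respectively. Written as one stop level, min(140, R + X), with X = 30: 120 at R = 90; 140 at R = 110; min(140, 160) = 140 at R = 130.

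**Step 5. Restart level = min(140, R + Y)**

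| Assumed R | Y = 10 | Y = 15 |
|---|---|---|
| 90 | 100 | 105 |
| 110 | 120 | 125 |
| 130 | 140 | 140 (145 before the cap) |

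**Step 6. Resting pressure above 140.** Section VI does not exclude a subject with managed hypertension who rests above 140 mmHg. The formulas in steps 4 and 5 give that subject no workable level: the stop is already met at rest and the restart cap lies below rest. The fix needs a separate provision for this case.

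**The case against.** The strongest reply is that the gap is narrow and its harm limited. A fixed ceiling is a defensible choice, and the symptom limb covers much of what lies below it. Each measured stimulus lasts 0.6-0.8 s, and the Protocol notes that "the duration of stimulation is very brief". Symptoms in the earlier trial subsided quickly on stopping. The same item says that lengthening the interval between stimuli minimises haemodynamic changes and that early AD signs resolve over the following 3-4 weeks. 'Stabilize' is ordinary clinical language, and leaving restart to judgement is understandable in a 16-subject study by an experienced team. Both R and X are assumed.

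Most of this stands, and it keeps the point minor. It does not supply the missing reference: a rule aimed at change still has no measure of change, for stopping or for restarting.

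Three stronger readings are tempting, and the documents do not support them.
- A reader might infer that subjects are unprotected below 140 mmHg, or that everything rests on staff. The symptom limb turns on what the subject experiences. It can be acted on by the subject, caregiver or staff, with pulse and pressure monitored at visits and in the initial home period.
- A reader might apply the earlier trial's rate of about 20% to the 16 subjects (0.20 x 16 = 3.2) and take about 3 as the number exposed to the gap. Those were subjects with AD symptoms, whom the second limb already stops. The rate says nothing about unrecognised rises, and it does not count restarts after symptom-free stops above 140 mmHg.
- A reader might infer an effect on the efficacy results. Nothing in either document links this rule to the efficacy analysis.

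**Conclusion.** The point holds as a minor safety fix. The stop rule does not do what its wording says: it names changes, measures a level, and leaves recovery undefined. On the number alone it allows a rise of up to 50 mmHg at an assumed resting 90 and 30 mmHg at 110, but stops a 6 mmHg rise from 135.

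The absence of a reference is read directly from the text and needs no assumption. The sizes rest on assumed resting pressures. How many subjects rest low, and how often a large rise would occur without recognised AD symptoms, cannot be derived from the documents.

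**What to change.** Keep 140 mmHg as a ceiling and reword the paragraph in the Protocol, section VIII, Precautions to minimize risks, item 3. Suggested text:

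> Resting systolic pressure will be recorded before the first stimulation of each hospital session and, during the initial monitored home period, before the first monitored stimulation of the day. Stimulation will be stopped if systolic exceeds 140 mmHg, or rises more than X mmHg above that resting value, or symptoms or signs of AD (including bradycardia) occur. It will resume only when symptoms have resolved and systolic is within Y mmHg of the resting value and no higher than 140 mmHg. If the resting value is itself above 140 mmHg, stimulation will not start until a study physician has reviewed the subject and set individual stop and restart levels.

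The sponsor's clinicians set X (illustrative 20 to 40) and Y, smaller than X. At home the caregiver is given one stop number for the day: the lower of 140 and R + X, or the physician's individual level if R is above 140. The guideline and discontinuation sentences stay, and eligibility is unchanged.

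**Cost.** One amended paragraph and two values to set. Pressure is already monitored in both settings, so no new visit or equipment is needed. The burden is one resting reading per session or monitored home day, plus repeat readings to confirm recovery. Subjects resting below 140 - X will have more pauses, and pauses after any stop may be longer. At home a pause means a short delay in using the system to cough. A subject resting above 140 mmHg waits for physician review.

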Spinal Cord Stimulation with Wire Leads to Restore Cough

IRB #: IRB15-00014

Date Approved: 4/10/2015

Spinal Cord Stimulation with Wire Leads to Restore Cough

IRB15-00014

NCT number 01659541

Date of the document: 11-23-2021

Title of the document: Study Protocol

Statistical Analysis Plan:

1. **Assessment of Expiratory Muscle Activation Parameters.** At each hospital out-patient visit, expiratory muscle assessments will be performed to measure airway pressure and peak expiratory airflow rates over a wide range of stimulus amplitudes. Curves will be constructed relating stimulus amplitude and stimulus frequency to airway pressure and peak expiratory airflow generation. These curves will be used to determine supramaximal stimulus paradigms (i.e. the lowest effective stimulus amplitude which results in maximal airway pressure and peak expiratory airflow generation). During each subject visit, the maximum airway pressure and peak expiratory airflow rate during spontaneous efforts and spinal cord stimulation (SCS) will also be recorded. Mean changes for the entire group will be determined. Since the magnitude of these parameters is affected by lung volume, it is important that airway pressure and peak expiratory airflow rate measurements be compared at the same lung volume. Measurements will be made at functional residual capacity (FRC) and total lung capacity (TLC), in the sitting posture. Each subject will be served as their own control.
2. **Assessment of Clinical Outcome Parameters.** The incidence of acute respiratory tract infections over a 2-year period will be collected prior to implantation of the study device. Following implantation, this will be tracked continually. Responses to questionnaires (life quality, caregiver burden, secretion management index) will be compared prior to implantation and also at defined endpoints during the study. Mean changes of each parameter for the entire group will be determined.
3. **Statistical Analysis.** Statistical analyses will be performed using a repeated measures analysis of variance. Each of the subjects will be served as their own control. Upon overall significance, appropriate pairwise comparisons will be performed. Since these contrasts are equivalent to multiple t-tests between levels, protection against type I error will be accomplished with a Bonferroni correction. A p value of < 0.05 will be taken as indicating statistical significance. Statistical significance, however, does not necessarily translate into clinical significance. Based upon numerous previous clinical studies, positive airway pressures of 40cmH₂O and peak airflow rates of 180L/min (3L/s) are considered effective in clearing secretions. This study will be considered successful, if SCS using wire lead electrodes will result in a) airway pressures and peak expiratory airflow rates that match or exceed these values and b) significant improvement in one or more of the clinical outcome parameters will be achieved.

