maximal cough effort in normal individuals. In contrast to MS and SS, this device is portable, does not require the repeated application of electrodes to the body surface, thereby avoiding potential skin injury, and is more likely to be effective in all patients, even obese individuals. Unfortunately, disc electrode placement requires a costly and invasive procedure significantly limiting general application. It should be emphasized that this technology is not commercially available. Wire leads have been in clinical use for several decades for control of pain and spasticity using a minimally invasive surgical procedure allowing for significant clinical advantages over disc electrodes. Based upon our extensive studies in animals and temporary, intra-operative placement of wire leads in humans, we have determined that SCS to restore cough can be accomplished with wire leads in a parallel arrangement.

Specific aims and hypotheses

The purpose of the study is to assess the utility of spinal cord stimulation to provide large positive airway pressures and expiratory airflow and simulate cough. Restoration of an effective cough in spinal cord injured (SCI) patients should reduce the incidence of atelectasis and respiratory tract infections and thereby reduce the high morbidity and mortality associated with respiratory complications in this patient population.

Hypothesis, therefore, that spinal cord stimulation (SCS) with wire leads, which can be inserted via minimally invasive techniques can a) be applied safely without the development of neural injury, b) result in sufficient activation of the expiratory muscles in persons with SCI to produce an effective cough mechanism, and c) have a significant clinical impact related to secretion clearance on subjects with SCI.

VI. Subject population

Number and description of subjects

We plan to evaluate 16 subjects of either sex. No subject will be excluded on the basis of race, religion or ethnic background. No pregnant women, children, prisoners, unconscious or incompetent people will be eligible.

Source and method of recruitment

Contact will be made via letter or phone call to potential research subjects made known to us through the assistance of the Spinal Cord Center at MetroHealth Medical Center, the General Clinical Research Center, and previously known subjects from other trials.

Service responsible for medical care

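### For airway pressure and peak flow, an omnibus F-test condition followed by plain Bonferroni gives up power that Holm would keep at the same 5% error; a cheap improvement that does not affect trial success

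*SAP*

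**What the plan says.** SAP section 3 sets out a three-step rule. The overall analysis is fixed first: "Statistical analyses will be performed using a repeated measures analysis of variance". Contrasts then depend on its result: "Upon overall significance, appropriate pairwise comparisons will be performed". Those contrasts are adjusted: "protection against type I error will be accomplished with a Bonferroni correction". The level is also given: "A p value of < 0.05 will be taken as indicating statistical significance". The protocol's Method of data analysis (section VII) repeats the second and third steps, without naming the overall test.

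The design is within-subject ("Each of the subjects will be served as their own control") and small ("We plan to evaluate 16 subjects of either sex"). SAP section 1 has pressure and flow measured at each out-patient visit, at FRC and at TLC, and adds that "the maximum airway pressure and peak expiratory airflow rate during spontaneous efforts and spinal cord stimulation (SCS) will also be recorded". It requires comparisons to be made at the same lung volume.

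Neither document gives the number of visits, the levels entering the ANOVA, the list of contrasts, the Bonferroni divisor, or whether the divisor spans pressure, flow and both lung volumes. No effect size, SD or power is given.

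**The concern.** A Bonferroni correction over a fixed family keeps the family-wise error at or below 5% whatever the F test shows. Requiring a significant F test first can therefore only remove declarations. Plain Bonferroni is also never better than Holm: Holm applies the same cut-off to the smallest p value and progressively less strict ones to the rest, needs no further assumption, and has the same 5% guarantee.

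Pressure and flow are the subject of the first primary aim, and the protocol wants the study to supply data for a multi-center trial. If results are read contrast by contrast (SCS against spontaneous effort, or one visit against another, at each lung volume), moderate real differences could go undeclared in 16 subjects although the same data would support them at the same error rate.

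**Working it through.** The plan has no power figure to reproduce, so the check compares decision rules on the same simulated data.

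**Inputs from the documents.** n = 16, paired; alpha 0.05 (two-sided assumed, since sidedness is not stated); F test, then Bonferroni.

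**Assumed inputs.** Five visits, compound symmetry with correlation 0.7, and a family of four contrasts, each later visit against the first. Effects are in units of the SD of the paired difference. There were 20,000 to 40,000 simulated trials per setting.

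**The rules with four contrasts.** Bonferroni compares every p value with 0.05/4 = 0.0125. Holm compares the ordered p values with 0.05/4 = 0.0125, 0.05/3 = 0.0167, 0.05/2 = 0.025 and 0.05/1 = 0.05, and stops at the first failure. As an invented illustration, p values of 0.010, 0.015, 0.020 and 0.030 give one declaration under Bonferroni and four under Holm.

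**Direct check of one contrast.** The paired t statistic has 15 df and noncentrality d × √16. For d = 0.8 this is 0.8 × 4 = 3.2. The two-sided critical value at 0.0125 is 2.837, giving power of about 64%; with no adjustment (0.05) the power is about 85%. Holm must lie between these two values.

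**Simulated power per contrast.**

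| True shift | As written | Bonferroni, no F condition | Holm, no F condition |
|---|---|---|---|
| 0.6 SD at all four later visits | 33.9% | 36.5% | 44.8% |
| 0.8 SD at all four later visits | 62.7% | 63.9% | 75.1% |
| 1.5 SD at all four later visits | 99.8% | – | 100% |
| 0.6 SD at last visit only | 34.4% | 37.0% | 37.1% |
| 0.8 SD at last visit only | 63.8% | 64.9% | 65.0% |
| 1.0 SD at last visit only | 85.9% | 86.1% | 86.2% |

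The chance that all four true contrasts are declared, as written against Holm, is 9.5% against 25.4% at 0.6 SD, 31.4% against 58.8% at 0.8 SD, and 64.8% against 87.1% at 1.0 SD.

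**Where the gain comes from.** At 0.8 SD on all four contrasts the total gain is 75.1 − 62.7 = 12.4 points: 63.9 − 62.7 = 1.2 from dropping the F condition and 75.1 − 63.9 = 11.2 from Holm. At 0.6 SD it is 10.9 points, split 2.6 and 8.3. For a change at the last visit only, the whole fix adds 37.1 − 34.4 = 2.7 points at 0.6 SD, 1.2 at 0.8 SD and 0.3 at 1.0 SD, almost none of it from Holm.

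**Error rates.** With no true difference, the family-wise error is about 4.6% for Bonferroni alone, 4.6% for Holm and 2.1% as written. With one or three true shifts, Holm stayed between 3.5% and 5.0%.

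**Sensitivity to the family.** If all pairs of k levels are tested instead (k = 3 to 6), Holm adds about 0.5 to 4 points over Bonferroni in most settings. The largest gain was about 10 points (74.9% to 84.8%, three levels in a linear trend totalling 1.5 SD, where the two adjacent contrasts are only 0.75 SD each). Dropping the F condition adds at most 1.3 points per contrast.

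**The case against.** Bonferroni after an ANOVA is valid and conservative, so preferring Holm is a choice about efficiency. That stands. So do four limits on what may be inferred.

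- *A reader might infer that paying for multiplicity twice is what loses contrasts.* It is not. The F condition costs about 0 to 3 points per contrast. Nor is it literally without effect on error: with no true differences it lowers the realised rate from 4.6% to 2.1%, though 4.6% was already acceptable. The Bonferroni step is not redundant either. Under all-pairs testing with one level truly different, the F test followed by unadjusted t-tests gave a family-wise error of about 12% with four levels and 28–30% with six.
- *A reader might infer that a late loss of response would be missed and the device would look more durable than it is.* The protocol's Device Malfunction section says fibrosis "could affect the long-term physiologic performance of the device", but as a risk statement. It adds that such damage was neither seen in the earlier trial nor much expected, and no aim, hypothesis or success criterion names durability. A decline at the last visit alone also gains little from the change. The large figures describe a shift at every later visit, which is close to Holm's best case.
- *A reader might infer that trial success is at risk.* In SAP section 3, criterion (a) uses fixed pressure and flow thresholds and criterion (b) uses the clinical outcomes. Neither is defined by pressure or flow contrasts.
- *The family is assumed.* Visit-against-first-visit contrasts are one plausible reading; the SAP speaks of group mean changes and lists none. Replacing Bonferroni by Holm without naming the contrasts would leave the rule just as underspecified.

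**Conclusion.** The point holds as a minor improvement. For any fixed family of pressure and flow contrasts, Holm without the F condition declares everything the written rule declares, and sometimes more, at the same 5% family-wise level; this needs no assumption about effects.

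The size does need assumptions. With n = 16, five visits, correlation 0.7 and four contrasts against the first visit, the gain is worthwhile when several contrasts are moderately non-null: at 0.8 SD on all four, about 63% to 75% per contrast and 31% to 59% for all four. It is small when only one contrast is non-null and nearly nil for contrasts of 1.5 SD or more, which SCS against spontaneous effort may well be. Under all-pairs testing it is usually a few points. The success criteria are unaffected.

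**What to change.** In SAP section 3 and the protocol's Method of data analysis, for airway pressure and peak flow:

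1. Name the contrasts, each within the same lung volume and at both FRC and TLC. State which outcomes and lung volumes share one family, so that the number of tests is known. Holm is no better defined than Bonferroni without this.
2. Remove the condition on the overall test, and test the named contrasts directly with paired t-tests under a Holm step-down correction at a two-sided family-wise 5%.
3. Keep the repeated measures ANOVA as a descriptive summary.

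Possible wording: *For airway pressure and peak expiratory flow, the contrasts listed in the table will be tested by paired t-tests with Holm adjustment within each listed family, regardless of the overall F test, which will be reported descriptively.*

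The cost is a short contrast list and two revised sentences, with no new data. The realised error moves nearer to 5% without exceeding it, and simultaneous confidence intervals are less simple to construct than with Bonferroni. The list should be fixed before the contrasts are run.

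### Must the plan name the lung volume, effort, visit and unit that decide whether stimulation reaches 40 cmH2O and 3 L/s?

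*SAP*

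**What the plan says.** SAP item 3 gives a success rule in two parts, both required. It begins "This study will be considered successful, if SCS using wire lead electrodes will result in" and its first part asks for "airway pressures and peak expiratory airflow rates that match or exceed these values". The values are an airway pressure of 40 cmH2O and a peak flow of 180 L/min (3 L/s). The second part asks for significant improvement in at least one clinical outcome.

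SAP item 1 describes the measurements:

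- **Visits:** "At each hospital out-patient visit, expiratory muscle assessments will be performed".
- **Lung volume:** "Measurements will be made at functional residual capacity (FRC) and total lung capacity (TLC), in the sitting posture". The SAP gives the reason for comparing like with like: "Since the magnitude of these parameters is affected by lung volume".
- **Effort:** maximum pressure and flow "during spontaneous efforts and spinal cord stimulation (SCS) will also be recorded".
- **Group summary:** "Mean changes for the entire group will be determined".

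The named test in item 3 is a repeated measures analysis of variance with Bonferroni-corrected pairwise comparisons. Protocol section VII (Specific Physiologic Measurements) adds a condition that the SAP does not mention: stimulation timed with the subject's own expiratory effort, which it describes as the way the system is to be used at home. The Protocol's data analysis section contains neither the thresholds nor the success rule.

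**The concern.** Half of the success verdict depends on a comparison with two fixed values, and the SAP does not say which of its many measurements enter that comparison. Pressure and flow are taken at two lung volumes, at every visit and, under the Protocol, under two stimulation conditions. The SAP itself says that lung volume affects the result. It also does not say whether the group mean, a proportion of subjects or every subject must reach the values.

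The planned group analyses seem aimed at a different question. Mean changes and contrasts address whether stimulation raises pressure and flow. They do not address whether the values under stimulation reach 40 cmH2O and 3 L/s. If results differed between FRC and TLC, or between the mean and the individual subjects, the same data could be called a success or a failure after they were seen.

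**Working it through.** **Inputs.** Thresholds: 40 cmH2O and 180 L/min (SAP item 3). Subjects: 16 (Protocol sections IV and VI). The documents give no mean, SD or correlation for pressure or flow under stimulation, so every such value below is an assumption.

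**1. The plan's own figure.** 180 / 60 = 3.0 L/s. The two forms of the flow threshold agree. Because pressure and flow are joined by *and*, both must pass, so a split between them is not open.

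**2. How many readings are open at one visit.**
- Two volumes x two stimulation conditions x two units (group mean or subjects) = 8.
- SAP item 1 lists only spontaneous effort and stimulation, and item 3 speaks of stimulation. Taking stimulation alone leaves 2 x 2 = 4.
- Item 1 summarises over the entire group. Taking the group mean leaves 2: FRC or TLC.

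No text narrows the lung volume or the visit. Stimulus amplitude is narrowed, because item 1 uses the amplitude curves to find the supramaximal setting.

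**3. Whether the planned work yields levels.** Item 1 records maximum pressure and flow under stimulation at each visit and plots both against amplitude. These are absolute values. A repeated measures analysis of variance on them also estimates condition means. In item 3, "Since these contrasts are equivalent to multiple t-tests between levels" refers to levels of a factor and does not restrict the analysis to changes. Only a written comparison of these values with 40 and 3 is missing.

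**4. Whether a change test could stand in for it.** Assume a baseline of 15 cmH2O, a mean rise of 15 and an SD of change of 15. With n = 16 the standardised rise is 15 / (15/4) = 4. Two-sided power at 0.05 is about Phi(4 - 1.96) = 0.98. The mean under stimulation would be 15 + 15 = 30, below 40. A significant change therefore does not establish the level. The plan does not claim that it does: part (a) is worded on the values themselves.

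**5. How much the unit could matter (pressure only, normal values, n = 16).** P(group mean reaches 40) = Phi((m - 40)/(s/4)). With p = Phi((m - 40)/s), P(all 16) = p^16, and P(at least 13 of 16) is the binomial tail.

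| Assumed mean m, SD s | Group mean | At least 13 of 16 | All 16 |
|---|---|---|---|
| 50, 15 | 0.996 | 0.396 | 0.010 |
| 60, 15 | 1.000 | 0.948 | 0.217 |
| 60, 25 | 0.999 | 0.551 | 0.022 |
| 80, 25 | 1.000 | 0.990 | 0.406 |

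The group mean and a 13-of-16 rule converge as the mean moves away from 40. The every-subject rule stays demanding, and no text suggests it.

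**6. What a stricter rule would do.** If the lower 95% limit had to clear each threshold, the observed mean would have to exceed it by t(0.975, 15)/sqrt(16) = 2.131/4 = 0.533 SD. The chance of passing on one measure is 0.465, 0.801 and 0.962 when the true mean lies 0.5, 0.75 and 1 SD above. For both measures, if independent, it is 0.465^2 = 0.22, 0.801^2 = 0.64 and 0.962^2 = 0.93; the single-measure figures are the limit at perfect correlation. This would be a new and harder criterion, not a clarification of the existing one. A subject count would be imprecise: 14 of 16 has an exact 95% interval of 61.7% to 98.4%.

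**The case for a change.** The strongest case for a change is that a success rule should be fixed before the data are seen, and this one is not fully fixed. Lung volume and visit are named nowhere. Effort and unit can only be inferred, and on effort the Protocol's home-use condition points away from the SAP's wording. The disc-electrode results in the Protocol suggest wide margins, but they come from another electrode, and whether wire leads match it is the hypothesis under test. One sentence in the SAP would close the matter at almost no cost.

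Most of this stands as description. The rule is incomplete, and one more sentence would be tidy. It does not show that the plan goes wrong. The remedy would ask the sponsor to write down choices that remain the sponsor's to make. Adding confidence intervals and a count of subjects reaching both values would enrich the report without altering the success rule, and requiring the intervals to clear the thresholds would replace it. Item 3 introduces the two values just after warning that statistical significance need not mean clinical significance, so they serve as clinical benchmarks. The setting is a 16-subject study, each subject their own control, meant to inform a multi-center trial. With so few subjects, results for every condition can be shown in full, so a mixed result would be visible.

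**Conclusion.** No change to the plan. Criterion (a) leaves out detail that analysts can supply sensibly: take the values recorded under supramaximal stimulation, set the group means beside 40 cmH2O and 3 L/s at both FRC and TLC, and show the individual subjects. The thresholds are explicit and consistent in units, the measurements are already planned, and no stated rule or figure is shown to give a wrong answer.

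On the natural reading, the open choice at a given visit is between two lung volumes. The visit itself is also unnamed. The widest count of 8 readings includes an effort condition that the SAP never mentions, and the largest differences in probability come from an every-subject rule that no text supports. Those probabilities rest on assumed means, SDs and normality.

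The conclusion assumes that the report shows both lung volumes and the stimulation conditions measured, not one favourable cell. If the means lay close to the thresholds, or FRC and TLC disagreed, a plain claim of success would need qualifying in the report.
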